8.5.1. Endpoints/Variables

To assess the time invariance dose accumulation, the statistical analysis will be based on the ratio of AUC(0-tau) (i.e., AUC(0-12) if dosing is BID or, AUC(0-8) if dosing is TID) on day 10 to AUC(0-∞) on day 1, if data permits.

8.5.2. Summary Measure

The summary measure will be the point estimate and 90% CIs of mean difference of ‘AUC(0-tau) at Day 10 – AUC(0-∞) at Day 1’ based on the log-transformed data and after back-transformation of this estimated difference, the geometric mean of the ratio ‘AUC(0-tau) at Day 10 : AUC(0-∞) at Day 1’ will also be presented.

8.5.3. Population of Interest

This analysis will be based on the PK population.

8.5.4. Strategy for Intercurrent (Post-Randomization) Events

In the Table 6 below, the possible intercurrent events and the rationale for relating them to treatment or otherwise is described. Once a subject discontinues from study treatment, they will proceed straight to follow up and no further data will be collected.

All subjects' data will be included in data listings irrespective of the strategies followed for the analysis.

If feasible, subjects will be replaced until the desired sample size is attained.

Table 6 Strategies for Intercurrent events

Intercurrent events	Relation to treatment and rationale	Strategy, rationale and details of action taken
Subject withdraws study consent	Not related to treatment/ Subject drops out due to logistic reasons and not due to any event related to treatment	
 - The strategy will be a While-on-Treatment strategy, where we are interested in the treatment effects prior to the withdrawal only. - Subjects' data available up to the withdrawal will be included in the time invariance accumulation rate analyses. - If a subject withdraws consent during a period, the missing data post withdrawal will not be imputed. - The derived PK parameters for e.g., AUC, C_{max} etc. of that partially completed period

		will be calculated if data permits (See section 8.1.1.2 Derived Pharmacokinetic Parameters for details on derivation criteria).
Subject does not take the full treatment	
Not related to treatment/
 
The treatment will be administered as a powder dissolved in diluent. To ensure all treatment is ingested, the bottle containing the dispersion will be rinsed three times and the subject will be expected to ingest this in addition to the initial dispersion. If three rinses are not all ingested, the subject may not take the full treatment dose.
	
In the current formulation, it is hard to measure the exact proportion of dose ingested if not all rinses are taken. It is also uncertain whether the formulation could change in future development. To account for this, we propose two different strategies described below. If this intercurrent event is not observed, then both strategies will provide the same results and only the hypothetical strategy will be presented for the final analysis.
 
Primary analysis
 
 - The strategy will be a Hypothetical strategy, where we are interested in the treatment effects in a hypothetical scenario where all subjects have taken complete dose. - In this case, the data from a period in which an incomplete dose is taken would be considered as missing at random and excluded from analyses. - If the drug formulation is changed in the future studies, this estimate will provide the true relationship between the actual dose intake and its exposure under this strategy. 
Supplementary analysis
 
 - The strategy will be a Treatment policy strategy, where we are interested in the treatment effects regardless of the actual amount of dose taken. - The analysis will include PK parameters derived based on concentrations of both complete and partial doses (if data permits based on criteria described in Section 8.1.1.2) and will be analysed using the nominal or prescribed dose. - If the drug formulation remains unchanged in the future studies, this estimate will provide the true relationship between a nominal dose and its exposure under this strategy, i.e. close to a real-world setting.

Subject drops out due to Adverse events	Related to treatment/ If the adverse event is confirmed to be related to study treatment	
 - The primary strategy will be a Hypothetical strategy, where we are interested in the treatment effects in a hypothetical scenario where discontinuation due to an AE would not happen. - The missing data after discontinuation will be assumed to be missing at random - The derived PK parameters of the last fully or partially completed period will be calculated if data permits (See section 8.1.1.2 Derived Pharmacokinetic Parameters for details on derivation criteria).
---	---	--

8.5.5. Statistical Analyses / Methods

Details of the planned displays are provided in **Error! Reference source not found.**: List of Data Displays and will be based on GSK Data Standards and statistical principles. Graphical presentations will be provided if appropriate. All data will be listed.

8.5.5.1. Statistical Methodology Specification

The following statistical analyses will only be performed if sufficient data is available (i.e. if subjects have well defined plasma profiles).

Pharmacokinetic analysis will be the responsibility of the Clinical Pharmacology Modelling and Simulation Department, (CPMS) and Statistical analyses of the pharmacokinetic parameters will be the responsibility of the Biostatistics Department.

Statistical analysis for time invariance ratio of GSK3186899 – Repeat dose study part	
Endpoint / Variables	

 • Ratio of AUC(0-tau) on day 10 to AUC(0-∞) on day 1 
(This will be calculated only if AUC(0-∞) on day 1 is appropriately estimated)
	
Model Specification	

 • Will be statistically analysed using a mixed model (MM) using a \log_e-transformation. The mixed model will contain: 
 ○ Fixed effects: day ○ Random effect: Subject • AUC(0-∞) on day 1 will be the reference phase in the analysis, while AUC(0-tau) on day 10 will be the test phase for BID (or, TID) regimen respectively, using \log_e-transformed AUC. • The Kenward and Roger method for approximating the denominator degrees of freedom and correcting for bias in the estimated variance-covariance of the fixed effects will be used. • An unstructured type of the covariance matrices G (accounting for the between subject variability) will be used. 	

- Based on the intercurrent events observed in the study, appropriate strategies from Table 6 in Section 8.5.4 will be considered for handling of missing data (if any) and interpretation of the analysis results. If multiple intercurrent events are observed (for e.g., if the subject does not take the full treatment as well he withdraws study consent), then the data will be handled using more than one strategy as described in Table 6 and interpretations of the results will be made accordingly.

Model Checking & Diagnostics

- For the Mixed Model, model assumptions will be checked, and appropriate adjustments may be applied based on the data.
- Distributional assumptions underlying the model used for analysis will be examined by obtaining a normal probability plot of the residuals and a plot of the residuals versus the fitted values (i.e. checking the normality assumption and constant variance assumption of the model respectively) to gain confidence that the model assumptions are reasonable.
- If there are any departures from the distributional assumptions, alternative transformations, such as data squared or square root of data, will be explored.
- Non-parametric analyses will be conducted if the normality assumption does not hold for any of the alternative transformations.
- If this model fails to converge, alternative covariance structures may be considered in the following order (1) Compound Symmetry (CS) and (2) Variance Components (VC).

Model Results Presentation

- The summary measure will be the point estimate and 90% CIs of mean difference of 'AUC(0-tau) at Day 10 – AUC(0-∞) at Day 1' based on the log-transformed data and after back-transformation of this estimated difference, the geometric mean of the ratio 'AUC(0-tau) at Day 10 : AUC(0-∞) at Day 1' will also be presented.

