8.4.5.1. Statistical Methodology Specification

The following statistical analyses will only be performed if sufficient data is available (i.e. if subjects have well defined plasma profiles).

Pharmacokinetic analysis will be the responsibility of the Clinical Pharmacology Modelling and Simulation Department, (CPMS) and Statistical analyses of the pharmacokinetic parameters will be the responsibility of the Biostatistics Department.

Statistical analysis for dose accumulation – Repeat dose study part	
Endpoint / Variables	

 • RAUC(0-tau) • RCmax • RCtau 	
Model Specification	

 • Will be statistically analysed using a mixed model (MM) using a \log_e-transformation. The mixed model will contain: 
 ○ Fixed effects: dose, day and dose*day ○ Random effect: Subject 	

Here dose denotes the total dose administered per day to a subject.
 
 • The Kenward and Roger method for approximating the denominator degrees of freedom and correcting for bias in the estimated variance-covariance of the fixed effects will be used. • An unstructured type of the covariance matrices R (accounting for the within subject variability) and G (accounting for the between subject variability) will be used. • Based on the intercurrent events observed in the study, appropriate strategies from Table 5 in Section 8.4.4 will be considered for handling of missing data (if any) and interpretation of the analysis results. If multiple intercurrent events are observed (for e.g., if the subject does 	

not take the full treatment as well he withdraws study consent), then the data will be handled using more than one strategy as described in Table 5 and interpretations of the results will be made accordingly.

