10.12.6. Pharmacokinetic Tables

Pharmacokinetic: Tables					
No.	Population	IDSL / Example Shell	Title	Programming Notes	Deliverable
Pharmacokinetic Concentration Data					
4.1.	PK	PK01	Summary of GSK3186899 Plasma Pharmacokinetic Concentration-Time Data - Part A		SAC
4.2.	PK	PK01	Summary of GSK3186899 Plasma Pharmacokinetic Concentration-Time Data - Part B		SAC
Derived Pharmacokinetic Parameters					
4.3.	PK	PK06	Summary of Non-transformed Derived GSK3186899 Plasma Pharmacokinetic Parameters by Dose - Part A		SAC
4.4.	PK	PK06	Summary of Non-transformed Derived GSK3186899 Plasma Pharmacokinetic Parameters by Dose - Part B		SAC
4.5.	PK	PK05	Summary of Log _e -Transformed Derived GSK3186899 Plasma Pharmacokinetic Parameters by Dose - Part A		SAC
4.6.	PK	PK05	Summary of Log _e -Transformed Derived GSK3186899 Plasma Pharmacokinetic Parameters by Dose - Part B		SAC
4.7.	PK	Non-standard PK_T1	Statistical analysis for comparison of food effect in Part A Cohort 3		SAC
4.8.	PK	Non-standard PK_T2	Statistical Analysis of Log Transformed Plasma GSK3186899 Pharmacokinetic Parameters Assessing Dose Proportionality (Power Model) – Part A		SAC
4.9.	PK	Non-standard PK_T3	Statistical Analysis of Log Transformed Plasma GSK3186899 Pharmacokinetic Parameters Assessing Dose Proportionality (Power Model) – Part B		SAC
4.10.	PK	Non-standard PK_T4	Statistical Analysis of Log-transformed Plasma GSK3186899 Parameters Assessing Steady-State – Part B		SAC

Pharmacokinetic: Tables					
No.	Population	IDSL / Example Shell	Title	Programming Notes	Deliverable
4.11.	PK	Non-standard PK_T4	Time invariance analysis of log-transformed Plasma GSK3186899 Parameters – Part B	Update the parameters for time invariance analysis	SAC

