A slope of 1 indicates the pharmacokinetics are dose proportional. A slope greater than 1 indicates the increase in PK is greater than proportional to dose.

USER ID:directory/program.sas 01JAN2002 12:01

Example : PK_T4

Population : Pharmacokinetic

Table 4.10

Statistical Analysis of Log Transformed Plasma GSK3186899 Trough Concentration Assessing Steady-State - Part B

[figure not shown]
Parameter (Units)	Treatment	Day 10		Day 1		Log- transformed Day 10 - Day 1	90% Confidence Interval	Back- Transformed Ratios	90% Confidence Interval
		n	LS Mean	n	LS Mean				
Ctau (ug/mL)	<Dose 1>	x	xx.xx	x	xx.xx	x.xx	(x.xx, x.xx)	x.xx	(x.xx, x.xx)
	<Dose 2>	x	xx.xx	x	xx.xx	x.xx	(x.xx, x.xx)	x.xx	(x.xx, x.xx)
	<Dose 3>	x	xx.xx	x	xx.xx	x.xx	(x.xx, x.xx)	x.xx	(x.xx, x.xx)
.....									

A Mixed effect model including dose, day and dose-by-day interaction as fixed effects and subject as a random effect is used to assess accumulation ratios. Unstructured covariance structures are used to describe within and between subject variabilities. A ratio of 1 indicates no accumulation. A ratio > 1 indicates drug accumulation.

USER ID:directory/program.sas 01JAN2002 12:01

Example : PK_F1
Population : Pharmacokinetic

Figure 4.7
Box Plot of AUC and Cmax versus doses (Linear) - Part A

Period 1 30 mg
Period 2 60 mg
Period 3 120 mg

Programming notes: this is an example shell to be updated to present each dose level.

USER ID:directory/program.sas 01JAN2002 12:01

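### The time-invariance model (SAP 8.5.5.1) has day as its only fixed effect, so it cannot fill the per-dose rows of the table shell assigned to it and returns only an average ratio over doses

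*SAP*

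**What the plan says.** **Model.** SAP 8.5.5.1 analyses log AUC with "Fixed effects: day" and "Random effect: Subject". Day 1 AUC(0-∞) is the reference and Day 10 AUC(0-tau) the test. There is no dose term and no day-by-dose term.

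**Target.** SAP 8.5.2 opens with "The summary measure will be the point estimate and 90% CIs of mean difference of" the two log AUCs. This is a single estimate, repeated under the results presentation in 8.5.5.1.

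**Display.** SAP 10.12.6 lists Table 4.11, "Time invariance analysis of log-transformed Plasma GSK3186899 Parameters – Part B", under shell PK_T4. Its only programming note is "Update the parameters for time invariance analysis". In SAP 10.13, PK_T4 has a row for each of three doses, each with Day 10 and Day 1 LS means, a log difference, a back-transformed ratio and 90% CIs. Its footnote reads "A Mixed effect model including dose, day and dose-by-day interaction as fixed effects and subject as a random effect".

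**Parallel analysis.** Accumulation uses the same Part B cohorts and the same two days. SAP 8.4.5.1 fits "Fixed effects: dose, day and dose*day", reports each dose, and adds a pooled ratio only if dose and day-by-dose are both non-significant and day alone is significant.

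**The concern.** The text and the table describe different analyses. If 8.5.5.1 is followed, the dose rows of Table 4.11 stay empty and its footnote misstates the model. If the shell is followed, the fitted model departs from the methods text.

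The choice also affects what can be learned. Time invariance is part of a named secondary objective, and section 8.5 averages over doses with no test, condition or reason given. Protocol 5.5.5 plans Part B doses at 0.5, 0.75 and 1 times the maximum anticipated therapeutic dose. If clearance changed over ten days at the top dose only, the planned estimate would dilute that change with the two lower doses.

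**Working it through.** The documents give no precision or power figure for this analysis, and Protocol 10.2 states that Part B was not sized statistically. There is therefore no plan figure to reproduce.

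**Inputs**
- Active subjects: 6 per dose, up to 3 doses, so up to 18 (SAP 2.3).
- Within-subject CV: 20% and 30%, the planning values for AUC and Cmax in Cohort 3 (Protocol 10.2). Using them as a range for Part B is an assumption.
- Half-life about 1.3 h (Protocol 5.4, SAP 10.4.1); absorption rate 0.7 per hour (Protocol Table 3).
- All true ratios below are assumptions.

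**1. What the day-only model estimates.** With complete pairs and equal numbers per dose, the day effect is the plain mean of the three per-dose log ratios.
- 1.0/1.1/1.3: exp[(0 + 0.0953 + 0.2624)/3] = exp(0.1192) = 1.13.
- 0.80/1.00/1.25: the logs sum to zero, so the result is 1.00.
- 1.0/1.0/1.5: exp(0.4055/3) = 1.14.

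For the interval, the variance of a subject's log ratio is 2·sw² + SS/17. Here sw = √ln(1+CV²) and SS = 6 × the sum of squared deviations of the three log ratios from their mean. For 1.0/1.0/1.5 at CV 20%, sw = 0.198 and SS = 0.658, so the variance is 0.0784 + 0.0387 = 0.1171. The half-width is 1.740 × √(0.1171/18) = 0.140, giving a 90% CI of 0.99 to 1.32 (0.95 to 1.38 at CV 30%). A 50% rise at the top dose appears as 14%, with an interval that includes 1. For 0.80/1.00/1.25 the interval is 0.87 to 1.15 at CV 20%.

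A check on 200 simulated data sets with ratios 0.80/1.00/1.25 gave 1.00 from the day-only model and 0.79/0.99/1.26 from the model with day-by-dose.

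**2. Precision of the two models when the true ratio is 1**

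| CVw | sw | Per dose: exp[1.753·sw·√(2/6)] | Pooled: exp[1.740·sw·√(2/18)] |
|---|---|---|---|
| 20% | 0.198 | ×/÷ 1.22 | ×/÷ 1.12 |
| 30% | 0.294 | ×/÷ 1.35 | ×/÷ 1.19 |

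**3. Is RAUC(0-tau) a substitute?** In a one-compartment model, the share of AUC beyond 12 h is (ka·e^(−12k) − k·e^(−12ka))/(ka − k), with k = ln 2/half-life. With no change in clearance, RAUC(0-tau) at steady state is 1/(1 − share), while the time-invariance ratio is 1.

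| Half-life | Share beyond 12 h | RAUC(0-tau) with constant clearance |
|---|---|---|
| 1.3 h (predicted) | 0.6% | 1.01 |
| 3 h (assumed) | 9% | 1.10 |
| 5 h (assumed) | 24% | 1.31 |

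The two ratios nearly coincide at 1.3 h. At longer half-lives RAUC(0-tau) mixes accumulation with any change in clearance.

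**4. Would the 8.4.5.1 pooling rule work here?** It requires a significant day effect. If the true ratio is 1 at every dose, a 5% test (level assumed) meets that condition in about 5% of trials at most. The dose term must also be non-significant, although the planned doses span a factor of two. Simulation with 6 subjects per dose, proportional exposure, between-subject CV 30% to 50% and within-subject CV 20% to 30% (all assumed) released a pooled ratio in about 1% to 3% of trials.

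**5. Power of the interaction test.** For 0.80/1.00/1.25, a 5% test of day-by-dose has about 60% power at CV 20% and 31% at 30%. A non-significant interaction is weak support for pooling, so the per-dose estimates matter more than the test.

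**The case against.** The strongest reply is that one pooled ratio is what 8.5.2 asks for, whereas the accumulation text explicitly asks for results by dose. PK_T4 is drawn for Table 4.10: its title names trough concentration and its footnote speaks of accumulation ratios. An example shell that was not fully adapted is at least as likely as a wrong model. The protocol specifies no time-invariance model, so nothing there is contradicted. This stands as an account of how the mismatch may have arisen. It does not remove the mismatch, because the programming note changes the parameters and leaves the dose rows and footnote in place.

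A reader might infer that a dose-dependent change would be lost to the study. The documents do not support that. Accumulation is estimated per dose, the shell for Table 4.9 gives dose-proportionality slopes for Day 1 and Day 10 separately, Part B parameters are summarised by dose, and individual values are listed. At a 1.3 h half-life the per-dose RAUC(0-tau) is almost the same quantity. This holds less well if the half-life proves longer, and SAP 10.4.1 itself provides for one above 5 h.

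A reader might also infer that leaving out dose biases the ratio when Day 1 AUC(0-∞) is missing for some subjects. That is not supported either. Section 8.5.5.1 calculates the ratio only where Day 1 AUC(0-∞) is adequately estimated, which reads as complete pairs, and each subject's dose then cancels. Nothing in the documents points to losses concentrated at the top dose.

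**Conclusion.** The concern holds as a minor inconsistency with a limited analytic consequence. The model in 8.5.5.1 cannot produce the per-dose rows of Table 4.11, and what it does produce is a geometric mean over doses. The cause is the missing day-by-dose term; leaving out the dose main effect alone does no harm with complete pairs.

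The averaging can be material within this analysis: a 50% rise at one of three doses is reported as 14%. That figure rests on assumed true ratios, 18 active subjects with complete pairs, and planning CVs carried over from Cohort 3. For the study as a whole the loss is small if the half-life is near 1.3 h, and larger if it is several hours. The pooled estimate is not wrong as an average, and the primary safety objective is not affected.

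**What to change.** In SAP 8.5.5.1, fit dose, day and dose*day with subject as random, as in 8.4.5.1. Report the ratio and 90% CI for each dose in Table 4.11. Also report the pooled ratio named in 8.5.2 in every case, as an equally weighted average over doses, and do not make it conditional on the 8.4.5.1 significance rule. Adapt the title, parameters and footnote of PK_T4 for Table 4.11.

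If a single pooled ratio is truly all that is wanted, say so with a reason, and remove the dose rows and the dose terms from the Table 4.11 shell.

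Either way the cost is SAP wording and programming, with no new data. The drawback of the preferred change is the wider per-dose limits shown in the working; the pooled ratio remains available beside them.

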10. APPENDICES

10.1. Appendix 1: Protocol Deviation Management and Definitions for Per Protocol Population

10.1.1. Exclusions from Analysis Population

Per protocol population is not defined in this protocol.

Important protocol deviations and violations of the inclusion and exclusion criteria will be listed.

10.2. Appendix 2: Schedule of Activities

10.2.1. Protocol Defined Schedule of Events in PART A (Cohorts 1-3)

Procedure	Screening (Up to 28 days before Day 1)	Study Period (Days)					Follow-Up (14-21 days post last dose) /Early Withdrawal	Notes
		-1	1	2	3	4		
Outpatient Visit	X						X	
Admission to Clinical Unit		X						
Inpatient Stay at Clinical Unit			←=====X=====→					
Discharge from Clinical Unit					X			Following completion of all assessments.
Informed Consent	X							
Inclusion and Exclusion Criteria	X							
Demography	X							
Full Physical Examination	X							Additional exams/screens may be performed, or brief exams made full exams, by the Investigator, as deemed necessary (e.g. where safety or laboratory findings indicate). Tests will be conducted within site specified standards.
Brief Physical Examination		X	X		X	X		
Drug/Alcohol/Smoking Screen	X	X						Tests include alcohol breath test, smoking breath test and urine drug screen.
Medical/Medication/Drug/Alcohol History	X							
HIV, Hepatitis B and C Screening	X							
FSH + Oestradiol	X							Females only, if required
Holter Monitoring (48 hours)	X							
Haem/Chem/Urinalysis Test (Include Liver Chemistries)	X	X	X		X	X		If trace protein in urine is detected, a repeat test can be performed (within 24 hours). If tests are considered abnormal, further quantification is required. Non-fasted samples can be collected on Day -1 and the Follow-Up Visit. All other samples to be collected in a fasted state.
Urine Sampling (metabolism)			X	X				A urine sample will be taken pre-dose (approx. 20mL) All urine from each participant will be collected from 0-24 hrs post dosing. Details of urine collection and processing are described in the SRM.

Procedure	Screening (Up to 28 days before Day 1)	Study Period (Days)					Follow-Up (14-21 days post last dose) /Early Withdrawal	Notes
		-1	1	2	3	4		
Safety biomarkers (KIM1, NGAL, Urinary albumin)			X	X				First urine sample of the morning to be collected (Day 1 sample collection should be pre-dose). Additional samples may be collected, as deemed necessary by the Investigator (e.g. where safety or laboratory findings indicate).
PK Blood Sampling			X	X				PK blood samples to be taken pre-dose on Day 1 and then at the following time points post first-dose: 10min, 30min, 1hr, 1.5hr, 2hr, 2.5hr, 3hr, 4hr, 5hr, 6hr, 8hr, 10hr, 12hr, 24hr. The time points stated may be modified depending on emerging SAD PK information as appropriate. Blood volumes to be collected include 2 mL for all time-points from pre-dose to 10 hrs, and 5 mL for time-points 12hr and 24 hr.
12-Lead ECG	X	X	T	X	↔X↔			Vital signs to include HR, BP, temperature and respiration rate. BP will be conducted in both a supine and standing position if participant develops any signs/symptoms which in the investigator's opinion are suggestive of adrenal insufficiency.
Vital Signs	X	X	T	X	↔X↔	X		12-Lead ECG and Vital Signs to be conducted on Day -1 and pre-dose on Day 1 and then at the subsequent time points post-dose: 30 min, 1 hr, 1.5hr, 2hr, 2.5hr, 4hr, 8hs, 12hr, 24 hr, 48 hr Timings will be reviewed as cohorts progress and may be adjusted to ensure appropriate measurements relative to peak concentrations for subsequent cohorts. T = Triplicate (for all assessments, except temperature and respiratory rate). If any abnormal ECG reading is recorded, refer to Section Error! Reference source not found. for appropriate action.

Procedure	Screening (Up to 28 days before Day 1)	Study Period (Days)					Follow-Up (14-21 days post last dose) /Early Withdrawal	Notes
		-1	1	2	3	4		
Telemetry			←X→					Continuous at least 24hr post-dose. Initiate at least 15 min. prior to dosing.
Meals		X	X	X	X	X		
Fasting regimen: On Day 1, participants will have fasted 8hr overnight prior to dosing. An adapted standard breakfast will be served approximately 3 hours after dosing.
 
Fed regimen: On Day 1, participants will fast 8hr overnight and an adapted standard breakfast will be served approximately 30 minutes prior to dosing.
 
Meals will be served as per the site schedule on Days -1, 2, 3 and 4.
 
Water permitted on an ad lib basis up to 1hr before dosing. No water to be taken in the hour prior to dosing except for the liquid part of the adapted standard breakfast for the Fed regimen. At least 8 fl oz (240ml) to be taken 1 hour after dosing. No water to be taken in the hour after dosing except for the rinse of the dose.

Bile Sampling (Enteroto-test)			X					Cohort 3 only. Enteroto-test bile string swallowed 2 hr post-dose, after 5 hr the bile string will be removed.
Randomization			X					
Study Treatment			X					
AE Review			←=====X=====→		X			
SAE Review	X		←=====X=====→		X			
Concomitant Medication Review	X		←=====X=====→		X			

